### 3.0 LIST OF ABBREVIATIONS

AE	Adverse Event
ALT	Alanine Transaminase
AST	Aspartate Transaminase
CCI	██████████
CI	Confidence Interval
DENV	Dengue Virus
eCRF	electronic Case Report Form
ELISA	Enzyme-Linked Immunosorbent Assay
FAS	Full Analysis Set
GMT	Geometric Mean Titer
GSD	Geometric Standard Deviation
HCT	Hematocrit
IA	Interim Analysis
LS	Least Squares
MAV	Markedly Abnormal Value
MedDRA	Medical Dictionary for Regulatory Activities
MNT 50	Microneutralization Test 50%
PBS	Phosphate Buffered Saline
PCC	Platelet Cell Count
PCR	Polymerase Chain Reaction
PFU	Plaque Forming Units
PPS	Per-Protocol Set
PT	Preferred Term
SAE	Serious Adverse Event
SAP	Statistical Analysis Plan
SD	Standard Deviation
SS	Safety Set
SOC	System Organ Class
TDV	Takeda's Tetravalent Dengue Vaccine Candidate
WCC	White Cell Count
WHO Drug	World Health Organization Drug

## 4.0 OBJECTIVES

### 4.1 Primary Objectives

To assess the humoral immune responses to subcutaneously administered Takeda's Tetravalent Dengue Vaccine Candidate (TDV) in a subset of healthy subjects aged between 2 and <18 years and living in dengue endemic countries.

### 4.2 Secondary Objectives

#### 4.2.1 Immunogenicity

To assess seropositivity rates following subcutaneously administered TDV in a subset of healthy subjects aged 2≥ to <18 years and living in dengue endemic countries.

#### 4.2.2 Safety

To evaluate the safety of subcutaneously administered TDV in healthy subjects aged 2≥ to <18 years and living in dengue endemic countries.

### 4.3 Exploratory Objectives

CCI

## 4.4 Trial Design

This is a Phase II, double-blind, controlled, randomized trial that will enroll 1,800 healthy children aged 2≥ to <18 years old into 1 of the following 4 groups:

- **Group 1 (TDV 2-dose):** receiving a two-dose primary vaccination at Day 1 (M0:Month 0) and Day 91 (M3:Month 3) with the trial vaccine. These subjects will also receive a placebo injection at Day 365 (M12:Month 12).
- **Group 2 (TDV 1-dose):** receiving a one-dose primary vaccination at Day 1 (M0) with the trial vaccine. These subjects will also receive a placebo injection at Day 91 (M3) and Day 365 (M12).
- **Group 3 (TDV 1-dose with booster):** receiving a one-dose primary vaccination at Day 1 (M0) and booster vaccination at Day 365 (M12) with the trial vaccine. These subjects will also receive a placebo injection at Day 91 (M3).
- **Group 4 (Placebo Control):** receiving injections of placebo at Day 1 (M0), Day 91 (M3), and at Day 365 (M12).

Subjects will be randomized to these 4 groups in a 1:2:5:1 ratio as shown in [Table 4.a](#).

**Table 4.a Number of Subjects per Group**

Group	No. of Subjects	No. of Subjects in the Immunogenicity Subset
Group 1	200	100
Group 2	400	200
Group 3	1,000	200
Group 4	200	100
Total	1,800	600

Randomization will be stratified by age group based on the age at the time of informed consent:

1. 2 to 5 years of age, inclusive,
2. 6 to 11 years of age, inclusive, and
3.  $12 \geq$  to  $<18$  years of age

CCI

Safety evaluation will include documentation of Serious Adverse Events (SAEs) and identification of febrile episodes of potential dengue etiology in all subjects for the trial duration. In addition, all subjects in the immunogenicity subset will be provided with a diary card and will be instructed to record:

- Solicited local adverse events (AEs) for 7 days following vaccination (day of vaccination + 6 days). These will include:
  - infant/toddler/child  $< 6$  years: injection site pain, injection site erythema and injection site swelling.
  - adult and child ( $\geq 6$  years): injection site pain, injection site erythema and injection site swelling.
- Solicited systemic AEs for 14 days following vaccination (day of vaccination + 13 days). These will include:
  - infant/toddler/child  $< 6$  years: fever, irritability/fussiness, drowsiness and loss of appetite.
  - adult and child ( $\geq 6$  years): asthenia, fever, headache, malaise, myalgia.
- Unsolicited AEs for 28 days following vaccination (day of vaccination + 27 days).

Any subject with febrile illness (defined as temperature  $\geq 38^\circ\text{C}$  on 2 consecutive days) will be asked to return to the site for dengue fever evaluation. A dengue infection will be considered virologically confirmed by either positive polymerase chain reaction (PCR) or NS1 enzyme-linked immunosorbent assay (ELISA). A blood sample will be collected within  $\leq 5$  days after the

[figure not shown]
onset of fever to perform virological confirmation of dengue and for hematology and for biochemistry to assess the severity of infection.

Blood samples for the measurement of neutralizing antibodies (immunogenicity) will be collected from a randomly selected subset of 600 subjects (100 subjects in group 1 and group 4 and 200 subjects in group 2 and group 3). CCI [REDACTED]

[REDACTED] Samples for immunogenicity will be taken prior to vaccination and at intervals of 1, 3, 6, 12, 13, 18, 24, 36, and 48 months following the first vaccination. CCI [REDACTED]

A schematic presentation of the trial design is given in Figure 4.a.

**Figure 4.a Schematic of Trial DEN-204**

**Investigational Vaccine(s):**

The Investigational Product is TDV, a tetravalent dengue vaccine comprised of four recombinant, live attenuated dengue virus strains:

CCI [REDACTED]

**Control Vaccine:**

The placebo vaccine is Phosphate Buffered Saline (PBS).

Takeda's TDV and placebo vaccines will be administered by subcutaneous injection.

**Visit Schedule:**

Clinical trial visits will be performed on Day 1 (Month 0), Day 28 (Month 1), Day 91 (Month 3), Day 180 (Month 6), Day 365 (Month 12), Day 393 (Month 13), Day 540 (Month 18), Day 730 (Month 24), Day 1095 (Month 36), and Day 1460 (Month 48).

A schedule of procedures is listed in [Appendix A](#).

**Duration of Trial:**

For each subject, the duration of the trial will be 48 months and will include a total of 10 protocol-scheduled visits for subjects included in the immunogenicity subset and a total of 7 protocol-scheduled visits for subjects not included in the immunogenicity subset.

Interim analyses on cleaned safety and immunogenicity data CCI [REDACTED] are planned on data up to Month 6, and on data up to Month 18 (see Section [7.13](#)).

## 5.0 ANALYSIS ENDPOINT

### 5.1 Primary Endpoint

Geometric Mean Titers (GMTs) of neutralizing antibodies (Microneutralization Test 50% [MNT50]) for each of the four DENV serotypes at Months 1, 3, 6, 12, 13, 18, 24, 36, and 48.

### 5.2 Secondary Endpoint

The secondary endpoints for this trial are as follows:

#### Immunogenicity Endpoints:

Seropositivity rates (%) for each of the four DENV serotypes where seropositivity is defined as a reciprocal neutralizing titer  $\geq 10$  at Months 1, 3, 6, 12, 13, 18, 24, 36, and 48.

#### Safety Endpoints:

##### *Immunogenicity Subset:*

[figure not shown]
- Frequency and severity of solicited local (injection site) and systemic AEs for 7 and 14 days after each vaccination, respectively.
- Percentage of subjects with any unsolicited AEs for 28 days after each vaccination.

##### *All Subjects:*

- Percentage of subjects with SAEs throughout the trial.
- Percentage of subjects with febrile episodes of virologically confirmed dengue throughout the trial.

### 5.3 Exploratory Endpoints

CCI

## 6.0 DETERMINATION OF SAMPLE SIZE

This trial is designed to be primarily descriptive and is not based on testing formal null hypotheses. Therefore the sample size was not determined based on formal statistical power calculations. The number of subjects will provide a reasonable sample size for the evaluation of the persistence of immune responses following administration of a single TDV dose, and of the effect of a TDV booster dose, and to provide an adequate safety database prior to initiating Phase III studies.

### 6.1 Immunogenicity

For illustrative purposes, [Table 6.a](#) provides approximate 95% confidence interval (CI) for various different seropositivity rate estimates, given the planned sample size per group in the immunogenicity subset.

**Table 6.a Approximate 95% Confidence Interval in Seropositivity Rates ( $MNT_{50} \geq 10$ ) for the Planned Sample Size in the Treatment Groups**

Response Rate	(95% CI) N=100		(95% CI) N=200	
	LL	UL	LL	UL
50%	39.8%	60.1%	42.9%	57.1%
60%	49.7%	69.7%	52.9%	66.9%
85%	76.5%	91.4%	79.3%	89.6%

LL = Lower Limit, UL = Upper Limit

[Table 6.b](#) provides approximate 95% CI for various different GMT and Geometric Standard Deviation (GSD), given the planned sample size per group in the immunogenicity subset.

**Table 6.b Approximate 95% Confidence Interval in GMT of Dengue Neutralizing Antibodies for the Planned Sample Size in the Treatment Group**

GMT (GSD)	(95% CI) N=100		(95% CI) N=200	
	LL	UL	LL	UL
500 (6)	351.9	710.4	390.1	640.9
1500 (6)	1,055.8	2,131.1	1,170.2	1,922.8
200 (8)	133.1	300.6	149.9	266.8
50 (7)	34.1	73.2	38.2	65.5

LL = Lower Limit, UL = Upper Limit

### 6.2 Safety

[Table 6.c](#) illustrates the probability of observing 1 or more event, (e.g., any specific type of AE related to vaccine) for a range of assumed true but unknown event rates in the range of 0.33% to 4.0% (without considering the background incidence), for events that are assessed in all subjects.

Therefore, even with an event rate as low as 0.33%, there is a 99.5% chance that at least 1 such event will be observed in the trial. For AEs with event rate higher than 4.00%, there is a >99.9% chance to observe at least one such event.

**Table 6.c      Probability of Observing 1 or More Events for Assumed “True” Event Rate and Given Sample Size**

“True” Unknown Event Rate	Sample Sizes		
	N=1,600	N=1,000	N=200
0.33%	99.5%	96.3%	48.4%
0.50%	>99.9%	99.3%	63.3%
1.00%	>99.9%	>99.9%	86.6%
2.00%	>99.9%	>99.9%	98.2%
3.00%	>99.9%	>99.9%	99.8%
4.00%	>99.9%	>99.9%	>99.9%

N=number of subjects

## 7.0 METHODS OF ANALYSIS AND PRESENTATION

### 7.1 General Principles

This Statistical Analysis Plan (SAP) was developed based on International Conference on Harmonization E3 and E9 Guidelines, and information provided in Protocol DEN-204, Version 3.0 dated 23JUL 2015 [1].

All statistical analyses will be generated using SAS Version 9.2 or higher.

This document will provide the details regarding the definition of analysis variables and analysis methodology to address all trial objectives. No inferential analyses will be performed for this trial.

A blinded data review will be conducted prior to unblinding of individual subject's vaccination assignment. This review will assess the accuracy and completeness of the trial database, subject evaluability, and appropriateness of the planned statistical methods.

Immunogenicity and safety endpoints will be summarized descriptively (frequency and percent for categorical data; and number of subjects with non-missing observation, mean, standard deviation (SD), median, minimum and maximum for continuous data) by all relevant trial visits, if appropriate. In summary tables for categorical data for which categories are defined on the electronic Case Report File (eCRF), all categories will be presented as specified, even if the subject count within that category is zero. For other categorical data (e.g. adverse events and medications), only categories with at least one subject will be presented.

All data collected will be presented in the listings, sorted by trial group, site number, subject number, and date/time of the finding if applicable.

There will be no imputation for missing data with the exception of missing or partial dates (i.e. start and stop dates for AEs) and as specified in Section 7.12. Partial dates will be presented as they are in the listings. The partial dates of AEs will be imputed only to determine the relationship between the start date of those partial dates and the informed consent date, as well as the first dose date of the double-blind vaccination. The following methods will be used to impute missing or partial dates of the start date of AEs.

#### Month/year available and day missing:

If the month and year are the same as those in the first dose date, and the event is not indicated as a pre-treatment event, the first dose date is to be used to impute the AE start date.

If the month and year are the same as those in the first dose date, and the event is indicated as a pre-treatment event, the date prior to the first dose date is to be used to impute the AE start date.

If the month and year are different from those in the first dose date, then the first day of the month will be used for the start date.

### **Year available and month/day missing:**

If the year is the same as the year of the first dose, and the event is not indicated as a pre-treatment event, the first dose date is to be used to impute the AE start date. If the year is the same as the year of the first dose date, and the event is indicated as a pre-treatment event, the date prior to the first dose date is to be used to impute the AE start date. If the year is the same as the year of the first dose date, then set the start date as January 1st.

The imputation of partial end dates for AEs will consider information such as the last dose date, and whether the AEs are ongoing by the end of trial.

Minimum and maximum values will be presented using the same number of decimal places as the recorded data. Means, the least squares means (LS Means), and medians will be presented to 1 more decimal place than the recorded data. SD and SE will be presented to 2 more decimal places than the recorded data. The CI about a parameter estimate will be presented using the same number of decimal places as the parameter estimate (ie., 1 more decimal place than the recorded data). Percentages will be presented to 1 decimal place (e.g., 80.3%). All p-values will be rounded to 3 decimal places. If a p-value is less than 0.001, it will be reported as “<0.001”; if a p-value is greater than 0.999, it will be reported as “>0.999”.

### **Definition of Baseline and Windowing of Post Baseline Data:**

Baseline is defined as the last non-missing measurement taken before the first dose of vaccination. Trial Day 1 is defined to be the date of the first vaccination, as recorded on the CRF vaccination page. Other trial days are defined relative to the trial day 1, with Day -1 being the day prior to Day 1.

A windowing convention will be used to determine the analysis value for a given trial visit for observed data analyses and will be applied to immunogenicity data, vital signs, CCI [REDACTED]. The window definitions are defined below in **Table 7.a** by trial visit. The window conventions are consecutive and contiguous; that is, the lower or upper bound of the windows is the midpoint between 2 consecutive trial visits and all data are included.

If more than one result for a variable is obtained for a subject in a visit window, the result with the date closest to the scheduled/expected visit date will be used. In the event that two measurements within a given visit window are equidistant to the scheduled visit date, the later observation will be used.

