**Table 7.a Visit Windows for Immunogenicity and Safety Analyses by Visit**

Visit	Scheduled Trial Day	Visit Window (Trial Day)		
		Vital Signs b	Immunogenicity	CCI
Baseline a	≤ 1	≤ 1	≤ 1	CCI
Day 28 (Month 1)	28	2-59	2-59	
Day 91 (Month 3)	91	60-135	60-135	CCI
Day 180 (Month 6)	180	136-272	136-272	CCI
Day 365 (Month 12)	365	273-379	273-379	CCI
Day 393 (Month 13)	393	380-466	380-466	
Day 540 (Month 18)	540	≥ 467	467-635	CCI
Day 730 (Month 24)	730		636-912	
Day 1095 (Month 36)	1095		913-1277	
Day 1460 (Month 48)	1460		≥ 1278	

(a) Where time is available, the time of the collection must be prior to the first vaccination of trial drug. Day 1 observations taken after the first vaccination are considered post-baseline values

(b) Vital signs include: systolic blood pressure, diastolic blood pressure, heart rate, body temperature, height and weight.

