## Appendix A Schedule of Trial Procedures

**Table A-1 Schedule Trial Procedures for Immunogenicity Subset**

Procedure	Vacc 1	Post Vacc 1	Vacc 2	Post Vacc 2	Vacc 3	Post Vacc 3	Follow-up	Follow-up	Follow-up	Follow-up/ET	Unscheduled
Visit	1	2	3	4	5	6	7	8	9	10	NA
Trial Timelines	D1 (M0)	D28 (M1)	D91 a (M3)	D180 (M6)	D365 (M12) b	D393 (M13) c	D540 (M18) d	D730 (M24) e	D1095 (M36) f	D1460 (M48) g	
Time window		+5 days	± 15 days	± 15 days	± 15 days	+5 days	± 15 days	± 15 days	± 15 days	± 15 days	
Signed Informed Consent/Assent	X										
Medical History	X										
Demographics	X										
Assessment of eligibility criteria i	X										
Complete Physical Examination j	X										
Pregnancy Test k	X		X		X						
Brief symptom-directed physical assessment l		X	X	X	X	X	X	X	X	X	
Randomization	X										
Blood Sampling h	X	X	X	X	X	X	X	X	X	X	
Vaccine administration	X		X		X						
Injection site evaluation m	X		X		X						
Diary card n distribution	X k	X	X k		X k						
Diary card Collection and Review o		X l		X l		X l					
Safety Review Call p	X m	X m	X m	X m	X m	X m	X m	X m	X m	X m	
Concomitant medication q	X	X	X	X	X	X	X	X	X	X	X
Febrile illness assessment											X
Blood sample febrile illness r (4 ml)											X

Note: The double-line border following Month 6 and Month 18 indicates the interim analyses which will be performed on cleaned safety and immunogenicity data (CC1) up to Month 6 and up to Month 18, respectively; NA: not applicable; D: Day; M: Month; ET: Early termination; Vacc: vaccination.

a. 28 days Post Vacc 2, home visits may be done by the site staff in order to collect the diary card. Optionally, a phone call may be made to remind the subject to keep the diary card secure and bring to the site on the Month 6 visit.

b. D1 + 364 days

- c. 28 days Post Vacc 3 (Day 365 + 28 days)
- d. D1 + 539 days
- e. D1 + 729 days
- f. D1 + 1094 days
- g. D1 + 1459 days
- h. Blood sampling before vaccination for immunogenicity **CCI** (Protocol Section 9.1.6).
- i. Review of inclusion/exclusion criteria will be documented before first vaccination.

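### Month 12 and Month 13 immunogenicity windows are counted from dose 1 and ignore the actual date of injection 3, so a few schedule-compliant subjects have pre- and post-injection titers reported under the wrong visit

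*SAP*

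**What the plan says.** **Anchor.** SAP Section 7.1 takes the date of the first vaccination as Day 1. It adds: "Other trial days are defined relative to the trial day 1, with Day -1 being the day prior to Day 1". The windowing "will be applied to immunogenicity data, vital signs" and one further redacted item.

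**Windows.** They are contiguous, and "the lower or upper bound of the windows is the midpoint between 2 consecutive trial visits and all data are included". Table 7.a gives Month 12 (scheduled Day 365) as Days 273-379 and Month 13 (scheduled Day 393) as Days 380-466. The only condition in that table that refers to a vaccination is footnote (a), which protects the baseline against the first injection. Nothing comparable protects injection 3.

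**Choice within a window.** Where several results share a window, "the result with the date closest to the scheduled/expected visit date will be used". For ties: "In the event that two measurements within a given visit window are equidistant to the scheduled visit date, the later observation will be used".

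**Visit schedule.** Table A-1 places the third vaccination at Day 365 ± 15 days, with the immunogenicity sample taken before the injection. The Month 13 visit has a window of +5 days, and footnote c describes it as "28 days Post Vacc 3 (Day 365 + 28 days". The footnotes for Months 12, 18, 24, 36 and 48 count from D1 instead.

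**Use.** GMTs at Months 12 and 13 are part of the primary endpoint (Section 5.1). Only Group 3 receives active vaccine at injection 3 (Section 4.4).

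**The concern.** The Month 12 sample is meant to be the last one before injection 3, and the Month 13 sample the first one after it. What separates them is the injection, but Table 7.a separates them by a fixed calendar day. When the injection falls near the edge of its permitted range, that day no longer lies between the two samples. The nearest-date and tie rules can then select the wrong one.

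The two possible errors act in the same direction. A boosted titer reported as Month 12 raises the pre-booster GMT, and an unboosted titer reported as Month 13 lowers the post-booster GMT. In Group 3 both shrink the apparent booster response, so this is bias and not only noise. Section 6.0 names the effect of the booster dose among the purposes the sample size should serve, and data to Month 18 go into an interim analysis used to plan other trials (Section 7.12). In Groups 1, 2 and 4 injection 3 is placebo, so there the samples are only mislabelled around a placebo injection.

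**Working it through.** **1. Reproduce Table 7.a.** Upper bound = floor((scheduled day + next scheduled day)/2).

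- (28+91)/2 = 59.5 → 59
- (91+180)/2 = 135.5 → 135
- (180+365)/2 = 272.5 → 272
- (365+393)/2 = 379
- (393+540)/2 = 466.5 → 466
- (540+730)/2 = 635
- (730+1095)/2 = 912.5 → 912
- (1095+1460)/2 = 1277.5 → 1277

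All eight stated bounds are reproduced. The table's arithmetic is right; the weakness is the anchor.

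**2. List the permitted dates.** Injection 3 and its pre-injection sample: Days 365 - 15 = 350 to 365 + 15 = 380, which is 31 days. Month 13 sample: 28 to 33 days after the injection, which is 6 offsets. Pairs: 31 × 6 = 186.

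**3. Apply the Table 7.a windows, then nearest date, then later if tied.** The pairs that fail are:

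| Injection 3 | Month 13 sample | Shared window | Distance to scheduled day | Reported |
|---|---|---|---|---|
| Day 350 | Day 378 (+28) | Month 12 | pre 15, post 13 | post-injection titer as Month 12; Month 13 empty |
| Day 350 | Day 379 (+29) | Month 12 | pre 15, post 14 | same |
| Day 351 | Day 379 (+28) | Month 12 | pre 14, post 14 (tie) | later one chosen: same |
| Day 380 | Days 408-413 (+28 to +33) | Month 13 | pre 13, post 15-20 | pre-injection titer as Month 13; Month 12 empty |

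Failures: 2 + 1 + 6 = 9 of 186 (4.8%). Permitted visits at Months 1, 3, 6 and 18 all fall in their own windows.

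**4. Size in Group 3 (assumptions).** The SAP gives no distribution of visit days and no expected booster rise. Assume that all 186 pairs are equally likely, that the booster gives a common fold rise f, and that affected subjects are otherwise like the rest.

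- Affected subjects: 200 × 9/186 = 9.7, of which 200 × 3/186 = 3.2 have a post-injection titer as Month 12 and 200 × 6/186 = 6.5 have a pre-injection titer as Month 13.
- Share of wrong values among reported Month 12 titers: 3/(186 - 6) = 3/180 = 1.7%. Among reported Month 13 titers: 6/(186 - 3) = 6/183 = 3.3%.
- Month 12 GMT is multiplied by f^(3/180): 1.012 for f = 2, 1.023 for f = 4, 1.039 for f = 10.
- Month 13 GMT is multiplied by f^(-6/183): 0.978, 0.956 and 0.927 for the same f.

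**5. After the change.** If the Month 12 sample must precede injection 3 and Month 13 is windowed from the actual injection 3, 0 of 186 pairs are mis-assigned.

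**The case against.** **Footnote c could mean a fixed day.** Its bracket computes Day 365 + 28, and Sections 4.4 and 7.11.3 and Table 7.a all give Month 13 as Day 393. With the visit fixed at Day 393 to 398, no pair is swapped. A Day 380 pre-injection sample would still leave the Month 12 window, but it would lose to the true Month 13 sample, so Month 12 would only be empty. Against this, footnote c leads with 28 days after the third vaccination, whereas the footnotes for Month 12 and for Months 18 to 48 count from D1. The floating reading is the more natural one, but the count of 9 depends on it.

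**The expected visit date could mean injection 3 + 28 days.** The nearest-date rule speaks of a scheduled or expected date. If that is individual to the subject, the six Day 380 pairs select the right Month 13 sample and Month 12 is merely empty. The three Day 350 and 351 pairs still fail, because the fixed windows decide membership first and the tie rule refers only to the scheduled date.

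**The effect is small beside sampling error.** Table 6.b, for N=200, GMT 500 and GSD 6, gives 390.1 to 640.9, about -22% to +28%. That stands. The analysis is descriptive, and Section 7.10.1 plans estimates by visit with no formal Month 12-to-13 contrast.

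**Stronger readings that the document does not support.**

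- A reader might infer a larger effect from a normal spread of injection days. With an assumed SD of 10 days around Day 365 and samples at exactly +28, 8.9% of subjects would have Month 12 affected and 7.4% Month 13. But 12% of those injections lie outside Days 350-380. Counting permitted days only gives 2.8% and 1.3%, and the Month 12 figure falls to 0.7% when averaged over +28 to +33.
- A reader might infer that the affected subjects certainly stay in the primary PPS. Table 7.b has a sample-timing criterion for Month 1 only, but its missing-titer row for Months 1 to 18 does not say whether it means missing at any or at all of those visits. Under the first reading the emptied window removes the subject.
- A reader might infer that the trial was sized on the booster effect. Section 6.0 says there was no formal power calculation, and the booster is one of several purposes listed.

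**Conclusion.** The point holds in a limited form. On the leading wording of footnote c, 9 of 186 permitted date pairs give a wrong value for a primary endpoint visit, all with injection 3 on Day 350, 351 or 380. In Group 3 every such error understates the booster response.

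The size is modest. It is about 5% of Group 3 subset subjects if permitted days are uniform, and fewer if visits cluster near Day 365. The GMT shifts are about 1-4% upward at Month 12 and 2-7% downward at Month 13. These rest on the assumed uniform days and the assumed 2- to 10-fold rise, neither of which the SAP supplies.

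Whether the values reach the PPS depends on how the missing-titer row is read. They remain in the supportive FAS analysis either way, because the FAS asks only for a valid pre-dosing and at least one valid post-dosing sample. If that row means missing at any visit, the rule also drops fully compliant subjects from the PPS.

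**What to change.** In Section 7.1 and Table 7.a, for immunogenicity data:

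- End the Month 12 window at the date and time of injection 3.
- Start the Month 13 window after injection 3, with target day = actual date of injection 3 + 28 days.
- Apply the nearest-date and later-if-tied rules only within those bounds, so that no pre-injection sample can serve Month 13 and no post-injection sample can serve Month 12.
- Keep Table 7.a as it stands for subjects who do not receive injection 3.

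The SAP should also reconcile footnote c of Table A-1 with the fixed Day 393 given elsewhere, and say whether the missing-titer row of Table 7.b means any or all of the listed visits. The Month 3 window needs no change for permitted visits.

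The cost is SAP wording and derivation code. No new data are needed, and trial conduct does not change.
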